2.4.4.2 Analyses of secondary efficacy endpoints

2.4.4.2.1 Average change from baseline to Week 16-24 in pre-bronchodilator FEV1

Main statistical model and adjustment of covariates

The key secondary efficacy endpoint, the average change from baseline to Week 16-24 in the pre-bronchodilator FEV1 will be analyzed using a mixed-effect model with repeated measures (MMRM) approach. Model-based average across Weeks 16, 20 and 24 will be compared between the treatment groups. The dependent variable is the change from baseline in pre-bronchodilator FEV1 at each time point. The model will include sex, baseline height, smoking history (current vs. former smoker), baseline FEV1 value, treatment group, visit and treatment-by-visit interaction, baseline FEV1-by-visit interaction, the baseline eosinophil strata, and region (pooled countries) as covariates. An unstructured correlation matrix will be used to model the within-patient correlations. Parameters will be estimated using restricted maximum likelihood method with the Newton-Raphson algorithm. No imputation will be performed on missing FEV1 measurements.

Descriptive statistics including number of patients, mean, standard error, and least squares (LS) means will be provided for each treatment group. Difference in LS means and the corresponding two-sided 95% CI and p-value will be provided for the comparison. Sample SAS code can be found below:

```
proc mixed data=fevldata method=reml;
  class usubjid sex csmoker trt01pn cntygr1 eosbgpln avisitn;
  model chg = sex height csmoker trt01pn trt01pn *avisitn FEV1bl
  FEV1bl* avisitn cntygr1 eosbgpln avisitn
           trt01pn*avisitn /ddfm=kr residual;
  repeated avisitn / subject=usubjid type=un;
  lsmestimate trt01pn*avisitn 'Tx wks 16-24 avg minus pbo wks 16-24 avg' 0 0
1 1 1 0 0 -1 -1 -1/ divisor=3;
  lsmeans trt01pn*avisitn / pdiff cl e;
  ods output LSMeans=LSMeans Diffs=Diffs LSMEstimates=LSMEstimates;
run;
```

If the above model fails to converge, the specification may be changed as follows: 1) use maximum likelihood estimation instead of restricted maximum likelihood method; 2) specify a different covariance structure to reduce the number of unknown parameters to be estimated, the path will be UN→TOEPH→TOEP→AR(1).

MMRM model including measurements up to Week 52 will also be used to derive LS mean change at all time points measured. Differences in LS means, the corresponding 95% CI, and the p-value will be provided for comparison of SAR440340 versus placebo, along with descriptive statistics.

Similar analysis will be performed for the secondary efficacy population (high EOS group), without the baseline eosinophil strata in the model.

Sensitivity analyses

The following sensitivity analyses will be conducted to assess the robustness of the main model:

Analyses without imputation of the missing FEV1 data: these analyses will use the same MMRM model and estimation methods as specified above and include

- On-treatment analysis: In the case of premature discontinuation of study drug the analysis will include data up to 14 days after the last dose.

Analyses with imputation of the missing FEV1 data: these analyses will use the same MMRM model and estimation methods as specified above after missing data being imputed using the following methods

- Pattern-mixture multiple imputations: Missing pre-BD FEV1 values will be imputed multiple times using a regression model. The covariates to be included are sex, baseline height, smoking history (current vs. former smoker), baseline FEV1 value, treatment group, visit and treatment-by-visit interaction, baseline FEV1-by-visit interaction, the baseline eosinophil strata, and region (pooled countries). Forty imputations will be performed. For each imputation, the average change from baseline in pre-BD FEV1 to Weeks 16 to 24 will be analyzed. Statistical inference obtained from all imputed data will be combined using Rubin's rule.
- Control-based multiple imputations: Missing values will be imputed sequentially for each assessment time point using a regression model. Only estimate of the placebo group will be used to fit the MI models.

Similar analyses with imputation of the missing FEV1 data will be performed for the secondary efficacy population (high EOS group), without the baseline eosinophil strata in the model.

Technical details on the analyses with imputation of the missing FEV1 data are provided in [Appendix J](#).

Subgroup analysis

Subgroup analyses of the average change from baseline to Week 16-24 in pre-BD FEV1 will be conducted in the same subgroups as for the primary endpoint based on the primary MMRM model for pre-BD FEV1 described above. Within each subgroup, descriptive statistics including number of patients, mean, SD, and LS means will be provided for each treatment group. Difference in LS means and the corresponding two-sided 95% CI will be provided for the comparison of

SAR440340 and placebo within each subgroup. Treatment-by-subgroup interaction and its p-value will be derived from a MMRM model. The model covariates will include sex, baseline height, smoking history (current vs. former smoker), baseline FEV1 value, treatment group, visit, treatment-by-visit interaction, baseline FEV1-by-visit interaction, the baseline eosinophil strata, region, subgroup (if different from the aforementioned covariates), subgroup-by-treatment interaction, and subgroup-by-treatment-by visit interaction.

2.4.4.2.2 *Change from baseline to Week 24 in post-bronchodilator FEV1*

The analysis method for this endpoint is identical to the analysis of the key secondary efficacy endpoint, the average change from baseline to Week 16-24 in pre-BD FEV1, except that here we only have the value at Week 24, not at Weeks 16 and 20. Similar analysis will be performed for the secondary efficacy population (high EOS group), without the baseline eosinophil strata in the model.

2.4.4.2.3 *Time to first moderate or severe AECOPD*

Time to first moderate or severe AECOPD that occurs from randomization up to week 52 will be analyzed using a Cox regression model with treatment, baseline eosinophil strata and region (pooled countries), number of severe COPD exacerbations experienced in previous year (0 vs. 1+) at baseline, smoking history (current vs. former smoker) and post-BD FEV1 percent predicted (<50% vs. ≥50%) at baseline as covariates. The hazard ratio (HR) between SAR440340 and placebo along with its 95% confidence interval will be estimated by the Cox model. The Kaplan-Meier (K-M) method will be used to estimate the probabilities of first AECOPD at specific time points for each group. P-value from the log-rank test stratified by baseline eosinophil strata and region will be provided.

Time to first moderate or severe AECOPD is defined as (onset date of the first moderate or severe AECOPD-randomization date+1). If the patient did not experience any moderate to severe AECOPD events, the event time will be considered as censored at date of EOT or the last contact date within the planned treatment duration. Below is sample SAS code for the Cox regression model:

```
proc phreg data=ttevent;  
class trt01pn eosbgpln cntygr1 nscopd csmoker ppredFev1/ param = glm;  
model aval*cnsr(1) = trt01pn eosbgpln cntygr1 nscopd csmoker ppredFev1;  
estimate "SAR440340 vs Placebo"          trt01pn -1 1 / exp;  
ods output Estimates = Estimates;  
  
run;
```

Similar analysis will be performed for the secondary efficacy population (high EOS group), without the baseline eosinophil strata in the model.

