Pharmacokinetics																																											
Serum samples for SAR440340 concentration ^o		X	X	X		X		X		X				X																							X	X		X			
Anti-SAR440340 antibody ^p		X						X						X																								X			X		
Biomarkers																																											
Blood eosinophils and neutrophils	X	X		X ^q		X		X ^q						X																							X	X ^q		X			
Total IL33 and sST2 ^o	X	X		X		X		X						X																								X	X		X		
Calcitonin	X	X		X		X		X						X																								X	X		X		
PARC	X	X		X				X						X																								X					
Eotaxin-3	X	X		X				X						X																								X					
Total IgE	X	X		X				X						X																								X					
Fibrinogen	X	X												X																							X						
FeNO pre-bronchodilator (optional) ^f		X		X		X		X						X																													
FeNO post-bronchodilator (optional) ^f		X		X		X		X						X																													
Induced sputum (optional) ^s		X												X																									X				
Blood samples for RNA sample (optional)	X	X		X										X																									X				
Blood sample archival for exploratory research (optional) ^t	X	X		X				X						X																										X			

	S	R/ B																																		
VISIT	1	2 ^{a, b}	3	4	5	6	7	8	9	10	11	12	13	14	15	16	17	18	19	20	21	22	23	24	25	26	27	EOT ^c	F1	F2 ^d	EOS					
WEEK	W-4 to W-1	0	2	4	6	8	10	12	14	16	18	20	22	24	26	28	30	32	34	36	38	40	42	44	46	48	50	52	60	66	72					
DNA Pharmacogenomics analysis (optional)		X																																		
Efficacy																																				
COPD exacerbation reporting by the Investigator		X	X	X	X	X	X	X	X	X	X	X	X	X	X	X	X	X	X	X	X	X	X	X	X	X	X	X	X	X	X	X	X	X		
Spirometry (pre-BD) ^{u, v}	X	X	X	X		X		X		X		X		X		X		X		X		X		X		X		X		X		X		X		
Spirometry (post-BD) ^{u, v}	X	X	X	X		X		X					X							X								X				X		X		
EXACT ^w	Every day (diary) from screening to week 52																																			
SGRQ ^w		X		X		X		X						X						X								X		X		X		X		
EQ-5D-5L ^w		X												X														X		X		X		X		
Actigraphy Optional assessments (US/Canada only)	Co n- tin uous							Con- tinuos						Con- tinuos																						
At-home spirometry (FEV1) Optional assessments (US/Canada only)	BI D							BID						BID																						

S= Screening; R/B= Randomization/Baseline; F=Follow-up

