- u* Spirometry will be done locally according to European Respiratory Society (ERS)/American Thoracic Society (ATS) 2005 guidance but measured by a central laboratory. Spirometry will be performed during a trough period of bronchodilators according to their action duration, for example, withholding the last dose of salbutamol/albuterol or levosalbutamol/levalbuterol for at least 6 hours, withholding the last dose of ipratropium for at least 8 hours, withholding the last dose of LABA for at least 12 hours (ultra-long acting LABA like vilanterol should be withheld for at least 24 hours) and withholding the last dose of LAMA for at least 24 hours. This will be verified before performing the measurements. Note: When both pre and post-bronchodilator spirometry is assessed, the post-bronchodilator spirometry should be performed consistent with the mechanism of action of reliever (ie, 30 minutes for albuterol or other SABA).
- v* Following randomization and during the treatment period - if spirometry is not performed at the scheduled visit it should be performed at the following visit during the treatment period.
- w* The EXACT, SGRQ and EQ-5D-5L are to be completed in the patient's electronic diary.

- d* Electronic Diary will be used on daily basis for period of 12 weeks after ETD. The CAT assessment, and reliever medication will not be collected in patients after early treatment discontinuation.
- e* Complete physical examinations will include skin, nasal cavities, eyes, ears, respiratory, cardiovascular, gastrointestinal, neurological, lymphatic, and musculoskeletal systems.
- f* Vital signs, including systolic and diastolic blood pressure (mmHg), pulse rate (beats per minute), body temperature (°C), and respiratory rate will be measured at on-site visits. Body weight (kg) will be measured at EOT/EOS visits.
- g* ECG to be centrally collected & read.

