4 STUDY DESIGN

4.1 OVERALL DESIGN

Multinational, randomized, double-blind, placebo controlled, parallel group (2 groups), Proof of Concept (PoC) study that is designed to assess the efficacy, safety, and tolerability of SAR440340 in patients with moderate-to-severe COPD on an established LABA, LAMA and/or ICS background therapy (double or triple therapy). Patients will be treated with SAR440340 or placebo for a minimum of 24 weeks and up to a maximum of 52 weeks*, and a 20-week safety follow-up period.

**This study employs a variable treatment duration from 24 to 52 weeks to maximize data for the primary endpoint (annualized rate of exacerbation) in a time-efficient manner. Patients enrolled in the trial will remain in the treatment period for up to a maximum of 52 weeks or until the last patient randomized completes a minimum treatment period of 24 weeks. Of note, the accrual and drop-out rates will be closely monitored. If the accrual rates are significantly lower than planned and/or the drop-out rates are higher than expected, the minimum treatment duration may be extended to achieve the desired amount of total exposure. The maximum treatment duration of 52 weeks will not be changed.*

The study duration is outlined below:

- Screening period (10 days to 4 weeks)
- Randomized IMP treatment period (24 to 52 weeks)
- Post IMP safety follow-up treatment period (20 weeks).

The randomization/baseline Visit is defined as Day 1. The visit schedule should be adhered to within ± 3 days for the screening period and randomized IMP treatment period, and ± 5 days for the 2 visits during the post IMP treatment period.

At screening, patients must be on Standard of Care background therapy, for 3 months prior to Visit 2/Randomization and at a stable dose for at least 1 month prior to the Screening Visit 1, including either:

- Double therapy: LABA + LAMA or ICS + LABA or ICS + LAMA.
- OR
- Triple therapy: ICS + LABA + LAMA.

Patients who satisfy the inclusion and exclusion criteria will be randomized (1:1) to:

- SAR440340 (300 mg) administered as 2 SC injections every 2 weeks (q2w) for 24 to 52 weeks
- Matching placebo for SAR440340 administered as 2 SC injections q2w for 24 to 52 weeks

It is planned to enroll approximately 50% of patients on ICS-containing background therapy (ICS + LABA; ICS + LAMA or ICS + LABA + LAMA).

Patients must be willing to stay on their established background medication for COPD throughout the duration of the study.

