5.1 INCLUSION CRITERIA

Participants are eligible to be included in the study only if all of the following criteria apply:

Age

Participant must be 40 to 75 years of age inclusive, at the time of signing the informed consent.

Type of participant and disease characteristics

- I 01. Participants with a diagnosis of COPD for at least 1 year (based on Global Initiative for Chronic Obstructive Lung Disease [GOLD] definition, see (1)).
- I 02. Participants with moderate-to-severe COPD (post-bronchodilator FEV1/forced vital capacity [FVC] <70% and post-bronchodilator FEV1 % predicted <80%, but \geq 30%) at Visits 1 and 2.
- I 03. Participants with COPD Assessment Test (CAT) score \geq 10 at Screening Visit 1 and Visit 2/Randomization.
- I 04. Participants with reported history of signs and symptoms of chronic bronchitis (chronic productive cough for 3 months in the year up to screening in a patient in whom other causes of chronic cough [eg, gastroesophageal reflux, chronic rhinosinusitis, bronchiectasis] have been excluded).
- I 05. Participants with a documented history (eg, medical record verification) of \geq 2 moderate exacerbations or \geq 1 severe exacerbation within the year prior to screening
 - a moderate exacerbation is defined as an AECOPD requiring systemic corticosteroids (oral, intravenous, or intramuscular) and/or treatment with antibiotics (however, use of antibiotics alone does not qualify as a "moderate exacerbation" unless documentation is available that use of antibiotics was necessary for treatment of worsening symptoms of COPD)
 - a severe exacerbation is defined as an AECOPD that required a hospitalization.
- I 06. Participants with Standard of Care background therapy, for 3 months prior to Visit 2/Randomization and at a stable dose for at least 1 month prior to the screening, including either:
 - Double therapy: LABA + LAMA or ICS + LABA or ICS + LAMA.

OR

Triple therapy: ICS + LABA + LAMA.

I 07. Current or former smokers with a smoking history of ≥ 10 packs-year.

Weight

I 08. Body mass index (BMI) ≥ 18.0 kg/m² (inclusive).

Sex

I 09. Male or Female

See [E 28](#) for required contraceptive measures.

Informed Consent

I 10. Capable of giving signed informed consent as described in Appendix 1 ([Section 10.1.2](#)) which includes compliance with the requirements and restrictions listed in the informed consent form (ICF) and in this protocol.

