- A common standard deviation of 0.3 L in each of the two groups, which is a consensus value based on the review of historical data from COPD trials.
- A difference of 0.12 L between the treatment group and the placebo group.
- A 2-sided t-test with 5% significance level.
- Fifteen percent (15%) of patients with missing data at Week 24 due to discontinuation or other reasons.
- Patients are randomized to the treatment group and the placebo group with a 1:1 ratio.

With these assumptions, 170 patients per group (340 patients in total) will provide >90% power to detect a 0.12 L difference in FEV1 between the treatment group and the placebo group. The least significant difference between groups will be 0.07 L.

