2 STATISTICAL AND ANALYTICAL PROCEDURES

2.1 ANALYSIS ENDPOINTS

2.1.1 Demographic and baseline characteristics

The baseline value is defined as the last available value prior to the first dose of IMP. For patients randomized but not treated, the baseline value is the last available value up to randomization.

All baseline safety and efficacy parameters (apart from those listed below) are presented along with the on-treatment summary statistics in the safety and efficacy sections ([Section 2.4.5](#) and [Section 2.4.4](#)).

Demographic characteristics

The following demographic characteristics will be summarized separately by treatment and overall:

- Sex (Male, Female)
- Race (American Indian or Alaska Native, Asian, Black or African American, Native Hawaiian or Other Pacific Island, White, Multiple, Unknown, Not Reported)
- Age (years)
- Age groups (<60, ≥60-<65, ≥65-<70, ≥70-≤75 years)
- Ethnicity (Hispanic or Latino, non-Hispanic or Latino, Unknown, Not Reported)
- Region (East Europe: Poland, Russia, Turkey and Ukraine; Latin America: Argentina and Chile; Western Countries: USA, Canada, Australia and Germany)
- Body weight (kg)
- Body weight group (<70, ≥70-<90, ≥90 kg)
- Body mass index (BMI, kg/m²)
- BMI group (<25, ≥25-<30, ≥30-<35, ≥35 kg/m²)

Alcohol use will also be included in this summary as alcohol drinking frequency (Never, Occasional, At least daily, At least weekly, At least monthly) and number of standard alcohol drinks on a typical day when drinking (1 or 2, >2).

Medical or surgical history

Medical (or surgical) history includes all the relevant medical (or surgical) history during the lifetime of the patient.

This information will be coded using the version of Medical Dictionary for Regulatory Activities (MedDRA) in effect at Sanofi at the time of database lock.

COPD and allergic comorbidity medical history will be summarized separately, including:

- Hospitalization because of severe respiratory infection (Yes, No)
- Long stay in neonatal intensive care unit (Yes, No)
- Diagnosed with bronchopulmonary dysplasia (Yes, No)
- Family history of COPD (Yes, No)
- Exposed to occupational/environmental pollutants (Yes, No), if Yes, summarize years of exposure.

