2.5.4 Windows for time points

Visit windows based on days relative to the first IMP administration will be used to map the efficacy parameters (Table 6), selected safety variables (Table 7) and PK/PD variables (Table 8) to each scheduled visit. Date of randomization will be used as the reference date for patients not treated. The following rules will be applied:

1. For efficacy parameters, only scheduled measurements will be considered. If a patient has more than one measurement for the same parameter at different dates within the same visit window, the one that is closest to the target date will be used (or the latest in case of tie).
2. Only values from the central laboratory will be considered for laboratory variables.
3. For the same laboratory/vital sign/ECG/PK/PD parameter, if a patient has more than one measurement at different dates within the same visit window, the measurement that is closest to the target date will be used (or the latest in case of tie).
4. When a patient has more than one measurement on the same laboratory/vital sign/ECG/PK/PD parameter on the same date, then the one with the later/largest sample ID will be used.
5. For procedures planned on Visit 2, if it is done on the same date as the first IMP but the performance time is missing, it will be assigned to the Visit 2 time window.

Table 6 – Time window for efficacy endpoints

Visit	Target Day	Pre-BD spirometry	Post-BD spirometry
Visit 1 (Wk-4 to Wk-1)	-28±3	-28±3	-28±3
Visit 2 (Week 0)	1	≤1	≤1
Visit 3 (Week 2)	15	2-21	2-21
Visit 4 (Week 4)	29	22-42	22-42
Visit 6 (Week 8)	57	43-70	43-70
Visit 8 (Week 12)	85	71-98	71-126
Visit 10 (Week 16)	113	99-126	
Visit 12 (Week 20)	141	127-154	
Visit 14 (Week 24)	169	155-182	127-266
Visit 16 (Week 28)	197	183-210	
Visit 18 (Week 32)	225	211-238	
Visit 20 (Week 36)	253	239-266	
Visit 22 (Week 40)	281	267-294	
Visit 24 (Week 44)	309	295-322	
Visit 26 (Week 48)	337	323-343	
Visit 27 (Week 50)	351	344-357	
EOT (Week 52)	365	358-392	267-392
F1 (Week 60)	421	393-462	393-462
EOS (Week 72)	505	≥463	≥463

Table 7 – Time window for safety endpoints

Visit	Target Day	Vital signs	ECG	Hematology, biochemistry, urinalysis	Heptitis and HIV serology tests, quantiferon gold testing, serum pregnancy test	Urine pregnancy test
Visit 1 (Week -4 - 0)	-28±3	< -7	<-7	<-7	≤1	
Visit 2 (Week 0)	1	-7-1	-7-1	-7-1		≤1
Visit 3 (Week 2)	15	2-21				
Visit 4 (Week 4)	29	22-35				2-42
Visit 5 (Week 6)	43	36-49				
Visit 6 (Week 8)	57	50-63		2-84		43-70

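### The key secondary FEV1 model adjusts for one pre-dose FEV1 although two are collected; adding the Visit 1 value is a free gain in precision, of a size the documents do not fix

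*SAP*

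**What the plan says.** SAP 2.4.4.2.1 specifies the MMRM for the average change to Weeks 16, 20 and 24 in pre-bronchodilator FEV1: "The model will include sex, baseline height, smoking history (current vs. former smoker), baseline FEV1 value, treatment group, visit and treatment-by-visit interaction". The rest of the list adds baseline FEV1-by-visit, eosinophil stratum and region. The sample code has one FEV1 term, FEV1bl, and its visit interaction. The imputation models in the same section and in Appendix J also carry a single baseline value.

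SAP 2.1.1 defines that value: "The baseline value is defined as the last available value prior to the first dose of IMP".

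The schedule in protocol 1.3.1 places pre- and post-bronchodilator spirometry at Visit 1 and at Visit 2. One footnote covers all visits: "Spirometry will be performed during a trough period of bronchodilators according to their action duration", with central reading. Inclusion criterion I 02 in protocol 5.1 needs spirometry "at Visits 1 and 2", so Visit 1 data should be nearly complete. The screening period in protocol 4.1 lasts 10 days to 4 weeks.

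SAP Table 6 gives Visit 1 spirometry a window of Day -28±3 and Visit 2 a window of Day 1 or earlier. No efficacy model has a separate Visit 1 term.

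**The concern.** A single FEV1 reading contains visit-to-visit noise. Adjusting for one noisy baseline leaves part of that noise in the change score, and the same error is shared by Weeks 16, 20 and 24. Averaging those three visits therefore does not remove it, whereas a second pre-dose reading roughly halves it. The plan seeks precision by averaging three follow-up visits but does not use the second pre-dose reading that it already collects.

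At stake is a wider interval than the data allow on the key secondary endpoint. Post-bronchodilator FEV1 (2.4.4.2.2), FVC (2.4.4.3.1) and the high-eosinophil analyses reuse the model and inherit the loss.

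**Working it through.** **The plan's own figure.** Inputs from protocol 9.2 and SAP 1.3: "A common standard deviation of 0.3 L in each of the two groups", a difference of 0.12 L, two-sided 5%, 170 per arm and 15% missing.

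- Evaluable per arm: 0.85 × 170 = 144.5.
- SE = 0.3 × √(2/144.5) = 0.0353 L, and 0.12/0.0353 = 3.40.
- Power = Φ(3.40 − 1.96) = 92.5% (92.6% with 145 per arm). Protocol 9.2 states 92.6%.
- Least significant difference: 1.96 × 0.0353 = 0.069 L, against a stated 0.07 L.

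The inputs are read correctly. (Protocol 9.2 calls this endpoint post-bronchodilator FEV1; SAP 1.3 uses the same inputs for pre-bronchodilator FEV1. That is a separate matter.)

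**Model for the gain.** A pre-dose reading is X + e. A follow-up reading is X + D + e. X is the patient's level (SD sb), D the patient's true change (variance sD²) and e independent visit noise (variance sw²). The plan's SD fixes 2sw² + sD² = 0.09. The noise share is f = 2sw²/0.09. Neither sb nor f is in the documents; assumed ranges are 0.40 to 0.55 L and 25% to 100%.

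Variance per patient of the three-visit mean after adjustment:

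- one baseline: V = sD² + sw²/3 + sb²sw²/(sb² + sw²)
- two baselines: the same, with sw²/2 for sw² in the last term only

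Example, sb = 0.45 and f = 50%: sw² = 0.0225, sD² = 0.045, sb² = 0.2025.

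- One baseline: 0.045 + 0.0075 + 0.02025 = 0.07275.
- Two baselines: 0.045 + 0.0075 + 0.01066 = 0.06316.
- SE ratio: √(0.06316/0.07275) = 0.932, a fall of 6.8%.

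All four noise shares at sb = 0.45, with SE = √(2V/144.5):

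| Noise share | SE, L | SE falls by | Power, 0.12 L | Power, 0.08 L |
|---|---|---|---|---|
| 25% | 0.0337 → 0.0326 | 3.2% | 94.6 → 95.8% | 66.1 → 69.0% |
| 50% | 0.0317 → 0.0296 | 6.8% | 96.6 → 98.2% | 71.3 → 77.2% |
| 75% | 0.0295 → 0.0261 | 11.3% | 98.3 → 99.6% | 77.5 → 86.5% |
| 100% | 0.0268 → 0.0221 | 17.5% | 99.4 → about 100% | 84.8 → 95.2% |

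At 100% noise the fall is 16.8% for sb = 0.40 and 18.5% for sb = 0.55; lower shares hardly move with sb. The 0.08 L difference is an illustration and does not appear in the documents.

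A simulation of this model (2,000 runs, 290 patients) gave SEs of 0.0339 → 0.0331, 0.0309 → 0.0292 and 0.0268 → 0.0219 L at 25%, 50% and 100% noise. These are falls of 2.4%, 5.5% and 18.3%, with no bias.

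**Other correlation patterns** (also assumed), using V = (1 + 2rF)/3 − R². Here rF is the correlation among follow-up visits and R² is what the pre-dose values explain.

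- Equal correlation at all visits, 0.5 to 0.95: SE falls by 10.6% to 20.0%.
- Correlation 0.90 between the two pre-dose visits and among follow-up visits, with 0.70, 0.80 or 0.85 from pre-dose to follow-up: 3.0%, 5.9% or 9.5%.
- Stable patient level plus drift plus measurement error: about 3% to 12%.
- No stable patient level (pure decay): 0% to about 1%. The gain can also nearly vanish if Visit 1 tracks follow-up clearly worse than Visit 2. With correlations 0.65 against 0.70, and 0.90 elsewhere, it is 0.2%.

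**High-eosinophil population.** About 85 planned per arm × 0.85 = 72.25 evaluable. At 0.12 L and sb = 0.45, power moves 71.2 → 74.0%, 76.2 → 81.9%, 82.2 → 90.1% and 88.7 → 97.0% over the four noise shares.

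**Post-bronchodilator FEV1 at Week 24.** With one follow-up visit, sw²/3 becomes sw². Taking the same 0.3 L SD, the SE falls by 2.9%, 5.6%, 8.2% and 10.7%.

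**The case against.** The strongest case against is that nothing here is defective. One pre-dose baseline with a baseline-by-visit term is a valid analysis. Protocol 9.4.1 said that further covariates would be chosen on blinded data and documented in the SAP, and the SAP did so. SAP 2.4.4.4 makes all p-values nominal in this Phase 2a study, so no formal decision turns on a slightly narrower interval. At the planned 0.12 L, power is already about 95% to 99% under the model above. All of this stands. It limits the size and weight of the point but gives no reason to leave out a value already in the database.

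The top of the range also deserves doubt. A fall near 18% needs all change variance to be independent visit noise, with no true differences between patients in 24-week change, and Visit 1 to be as informative as Visit 2. Protocol 5.4 allows up to three attempts at screening, and rescreening when efforts are not reproducible, so Visit 1 may be somewhat noisier.

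Three stronger readings are tempting and not supported:

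- **That the estimate is biased.** Both readings precede dosing, and the randomised comparison is valid with either one or both.
- **That the stated power is wrong.** The 92.6% comes from an unadjusted single-visit t-test and reproduces.
- **That Visit 1 FEV1 is discarded outright.** Under the definition in SAP 2.1.1 and the Visit 2 window in Table 6, it becomes the baseline when Visit 2 is missing.

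**Conclusion.** The point holds as a free improvement. The key secondary MMRM uses one of two comparable pre-dose FEV1 values and so gives up some precision.

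The direction is well founded; the size is not known, because the documents give no visit-to-visit correlation. Under the stated assumptions the SE would fall by about 3% to 18%. A model with drift and measurement error gives about 3% to 12%, and wider assumptions span about 0% to 20%. At 0.12 L in all patients, power rises by only about 0.5 to 2 points. At the illustrative 0.08 L it rises by about 3 to 10 points, and in the high-eosinophil population at 0.12 L by about 3 to 8.

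**What to change.** Before unblinding, amend the SAP as follows.

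- **2.4.4.2.1:** add Visit 1 pre-bronchodilator FEV1 and its interaction with visit as covariates. Keep change from the existing baseline as the dependent variable, and keep the existing baseline terms.
- **2.4.4.2.2 and 2.4.4.3.1:** do the same with Visit 1 post-bronchodilator FEV1 and Visit 1 FVC.
- **Imputation models in 2.4.4.2.1 and Appendix J:** add the same Visit 1 value.
- **Identification:** take Visit 1 by its visit label. The Table 6 window of Day -28±3 misses the shorter screening periods that the protocol permits; those readings fall in the Visit 2 window, where only the one closest to Day 1 is kept.
- **Missing Visit 1:** substitute the Visit 2 value, so that no patient is lost.

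The cost is SAP wording and one more covariate with its visit interaction. No new data or patients are needed, and the endpoint does not change. If Visit 1 turns out to add nothing, the loss is a few degrees of freedom.

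### The sample LSMESTIMATE vector for the key secondary FEV1 contrast allows for five visits per arm, but the schedule has at least seven, so the code does not estimate the Week 16-24 difference it is labelled as

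*SAP*

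**What the plan says.** SAP 2.4.4.2.1 defines the key secondary contrast in words: "Model-based average across Weeks 16, 20 and 24 will be compared between the treatment groups". The response is the change from baseline at each time point, and no visit is excluded.

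The sample PROC MIXED code in that section lists `trt01pn` before `avisitn` in the CLASS statement. The contrast is requested by "lsmestimate trt01pn*avisitn 'Tx wks 16-24 avg minus pbo wks 16-24 avg' 0 0", completed on the next line by "1 1 1 0 0 -1 -1 -1/ divisor=3". The full vector is therefore 0 0 1 1 1 0 0 -1 -1 -1, divided by 3.

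SAP Appendix J (Change from baseline in FEV1, step 3) repeats this vector, and step 4 passes its output to PROC MIANALYZE. For the imputation analyses, 2.4.4.2.1 says that "these analyses will use the same MMRM model and estimation methods as specified above after missing data being imputed".

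SAP 2.5.4, Table 6, gives pre-bronchodilator spirometry windows at Weeks 2, 4, 8, 12, 16, 20 and 24 and then on to Week 52. The schedule in protocol 1.3.1 agrees on the visits up to Week 24.

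The SAP does not list the visits in the main model. It adds that "MMRM model including measurements up to Week 52 will also be used to derive LS mean change at all time points measured", which suggests that the main model stops at Week 24. Appendix J, however, imputes change at all visits without giving an end point.

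**The concern.** The vector's +1 and -1 blocks are five places apart. It therefore compares the same visits between arms only if each arm has exactly five visits, two of them before Week 16. The schedule has four visits before Week 16. Run as printed, the statement would return a different quantity under a label that reads correctly, and its coefficients still sum to zero.

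This is the only code supplied for the key secondary contrast, an endpoint with its own superiority hypothesis in protocol 9.1. The same model also serves the imputation sensitivity analyses, the high-eosinophil population and the subgroup analyses.

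**Working it through.** **Inputs.** The vector, CLASS order and divisor come from SAP 2.4.4.2.1, and the visits from SAP Table 6 and protocol 1.3.1. The planning difference of 0.12 L, SD of 0.3 L and 15% missing at Week 24 come from SAP 1.3. With `trt01pn` before `avisitn`, visit varies fastest within arm. Setting unlisted trailing cells to zero is an assumption about the software.

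**When the vector is right.** Take five visits per arm (Weeks 8, 12, 16, 20, 24). Cells 3-5 are Weeks 16, 20 and 24 of the first arm, and cells 8-10 are the same weeks of the second. The label holds, apart from its sign, which depends on level order. In general, with V visits per arm, a matched contrast in this cell order needs the two blocks V places apart. The printed gap is 8 - 3 = 5, so V must be 5.

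**Seven visits (Weeks 2-24), 14 cells.** Cells 3-5 are Weeks 8, 12 and 16 of the first arm. Cells 8-10 are Weeks 2, 4 and 8 of the second. Weeks 20 and 24 get no weight. The second arm's Weeks 16, 20 and 24 are cells 12-14, beyond the tenth coefficient whatever is done with unlisted cells.

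**Model to Week 52.** There are 15 visits by Table 6, or 14 without the Week 50 window. Either way cells 8-10 are Weeks 28, 32 and 36 of the first arm, so all six weights fall in one arm and there is no between-arm comparison.

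**Size with a true Week 16-24 benefit of 0.12 L and no drift.** The documents give no onset profile, so these are assumed:
- flat: 0.12 L at every visit
- ramp: 0.03, 0.06 and 0.09 L at Weeks 2, 4 and 8, then 0.12 L from Week 12
- late: zero until Week 16, then 0.12 L

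| Profile | 7 visits, SAR440340 first | 7 visits, placebo first | 15 visits, SAR440340 first | 15 visits, placebo first |
|---|---|---|---|---|
| Flat | (3 × 0.12)/3 = 0.12 | -(3 × 0.12)/3 = -0.12 | (0.36 - 0.36)/3 = 0.00 | 0.00 |
| Ramp | (0.09 + 0.12 + 0.12)/3 = 0.11 | -(0.03 + 0.06 + 0.09)/3 = -0.06 | (0.33 - 0.36)/3 = -0.01 | 0.00 |
| Late | (0 + 0 + 0.12)/3 = 0.04 | 0.00 | (0.12 - 0.36)/3 = -0.08 | 0.00 |

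**No effect, common linear drift d by Week 24 (assumed).** The result is (d/24) × (mean positive week - mean negative week).
- 7 visits: mean weeks 12 and 14/3 = 4.67, a gap of 7.33. For d = -0.02, -0.04 and -0.08 L this gives -0.006, -0.012 and -0.024 L.
- 15 visits: mean weeks 12 and 32, a gap of -20. The same drifts give +0.017, +0.033 and +0.067 L.

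**Type I error, 7 visits, d = -0.04 L.** Take 145 per arm (85% of 170 = 144.5) and an assumed common correlation ρ between visits. Then SE = √[2 × 0.09 × (1 + 2ρ)/(3 × 145)], which is 0.0288 L at ρ = 0.5 and 0.0315 L at ρ = 0.7. The shift of 0.0122 L is 0.42 or 0.39 SE, so the nominal two-sided 5% test rejects about 7% of the time.

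**Corrected weights.** A mean over Weeks 16, 20 and 24 in each arm, taken as SAR440340 minus placebo, returns 0.12 L for all three profiles and 0 under the null with drift.

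**Direction.** The contrast puts +1 on the first treatment level for treatment minus placebo. The Cox sample in SAP 2.4.4.2.3 uses "trt01pn -1 1 / exp" for SAR440340 versus placebo, with -1 on the first level. If `trt01pn` sorts the same way in both data sets, one of the two is reversed. The level order is not stated, so the documents do not show which.

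**The case against.** The code is labelled as a sample and stands beside a correct written definition, which a programmer should follow. It is clearly not ready to run: the interaction appears twice in the main MODEL statement, and Appendix J step 3 calls the model an ANCOVA, uses `chg12` as the response and omits smoking. The LSMEANS statement in the same code prints by-visit means and differences that could expose the error. All p-values are nominal (SAP 2.4.4.4). Table 6 assigns measurements to windows and is not a list of model visits, and the vector would fit a data set cut to Weeks 8-24. The Week 52 case is weak, because the SAP describes that as an additional model. The sizes rest on assumed profiles, drift and correlation, and the 7% figure applies Week 24 missingness to earlier visits.

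Much of this stands. The error is in code and not in the estimand, it could be caught, the Week 52 results are secondary, and no size can be fixed from the documents. None of it makes the vector correct. No text drops Weeks 2 and 4, the wording on each time point and on all visits points the other way, and the cell count needs no assumption about profiles.

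**Conclusion.** The concern holds. Ten positional coefficients cannot place weight on Weeks 16, 20 and 24 of both arms when each arm has seven visits, or more. That conclusion rests only on the printed vector, the CLASS order and the scheduled visits.

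What the statement would return instead also depends on zero-filling, level order and the visits in the model. Under the assumed profiles without drift, a true 0.12 L benefit comes out right in only one case: a flat effect, seven visits and SAR440340 coded first. The point should be fixed before programming. Whether the treatment direction is reversed remains an open query.

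**What to change.** - List the visits that enter the main MMRM and the Appendix J analysis model, and state the level order of `trt01pn`.
- In SAP 2.4.4.2.1 and Appendix J step 3, replace the vector with non-positional coefficients that identify arm and visit: Weeks 16, 20 and 24, SAR440340 minus placebo, divisor 3.
- Keep a positional vector only if both models are stated to hold exactly Weeks 2, 4, 8, 12, 16, 20 and 24. It is then 0 0 0 0 1 1 1 0 0 0 0 -1 -1 -1 with SAR440340 first, or the same with signs reversed if placebo is first.
- Align the treatment direction here, in Appendix J and in the Cox sample of 2.4.4.2.3 with the stated level order.

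The cost is one visit list, one level-order definition and a few lines of sample code. The estimand, the data collected and the conduct of the trial do not change.
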